10.1. Adverse Events

All reported AEs will be coded according to MedDRA.

An AE is defined as treatment-emergent, if first onset or worsening is after start of the first infusion of CUTAQUIG. Only treatment-emergent AEs (TEAEs) are accounted for in the analysis.

For each TEAE, the time relative to the start of the infusion will be calculated and the TEAE will be classified as temporally associated if the onset is during the infusion or within 72 hours after the end of the infusion.

All reported events will be listed and tabulated in full detail; in particular the following key statistics will be presented in a summary table:

- Total number of TEAEs reported.

Number of patients with

- Any TEAE
- Any drug related TEAE
- Any TEAE
- Any Drug Related TEAE
- Any Temporally Associated TEAE during Stabilization Period
- Any Temporally Associated TEAE during Treatment Period
- Any Local Site Reaction
- Any Severe TEAE
- Any Serious AE
- Product Withdrawn due to TEAE
- Study Discontinuation due to TEAE
- AE Outcome of Death

Also, the following TEAE tabulations of patient incidence will be presented:

- Temporally associated treatment-emergent adverse events during stabilization period by system organ class and preferred term
- Temporally associated treatment-emergent adverse events during treatment period by system organ class and preferred term
- Local site reaction treatment-emergent adverse events by system organ class and preferred term
- Treatment-emergent adverse events excluding local site reactions by system organ class and preferred term
- Serious treatment-emergent adverse events by system organ class and preferred term
- Serious treatment-emergent adverse events leading to study discontinuation by system organ class and preferred term
- Non-serious treatment-emergent adverse events by system organ class and preferred term
- Treatment-emergent adverse events leading to product withdrawal by system organ class and preferred term

- Treatment-emergent adverse events leading to early study discontinuation by system organ class and preferred term
- Treatment-emergent adverse events by highest relationship to treatment by system organ class and preferred term
- Treatment-emergent adverse events by maximum severity by system organ class and preferred term
- Infusion total flow rate and temporally associated treatment-emergent adverse events
- Infusion total flow rate associated with temporally related treatment-emergent adverse events- non-local site reactions
- Infusion total flow rate associated with temporally related treatment-emergent adverse events- local site reactions only
- Infusion total flow rate/number of lines associated with temporally related treatment-emergent adverse events- local site reactions only
- Percentage of infusions with one or more temporally associated TEAE

The following table listings of interest will be presented:

- Table listing of serious treatment-emergent adverse events
- Table listing of related treatment-emergent adverse events
- Table listing of related serious treatment-emergent adverse events
- Table listing of treatment-emergent adverse events leading to death
- Table listing of treatment emergent adverse events leading to study drug discontinuation
- Table listing of treatment-emergent adverse events leading to study discontinuation
- Table listing of local site reactions
- Table listing of treatment-emergent incidences of fever safety

Further, all AE data collected, including the infusion rate at onset of TEAE will be presented in by-patient listings.

Narratives will be prepared describing each death, other SAEs, and other significant AEs that are judged to be of special interest because of clinical importance

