1.2 Rationale for Conducting the Study

The administration of immunoglobulins via the SC route offers several advantages over IV infusion from a patient's and a physician's perspective. Replacement therapy by rapid SC infusion with a pump was introduced during the late 1980s. Several reports have shown that the SC method is feasible, safe, efficient, cost-effective, and highly appreciated by the patients.^[4,14-22]

Self-administration at home with small portable pumps or syringes can easily be learned by patients, which is another advantage of SC administered immunoglobulins (SCIG). It may remarkably improve the patient's quality of life and compliance as it reduces the frequency of hospitalizations and the need for in-home health care visitations. Administration of IgG via the SC route provides more stable and well-balanced IgG plasma levels until the end of the treatment interval, in contrast with the peak IgG plasma concentrations attained with IVIG solutions which weaken at the end of dose. When effective IVIG therapy cannot be continued because of the lack of peripheral and central vein access, SCIG might also be an alternative treatment option.

Patients may desire dosing flexibility to accommodate their personal schedules or reduce the number of injection sites; therefore, this study is investigating modified dosing regimens. These modifications include dosing at higher infusion rates to shorten the duration of infusions, dosing every other week (rather than every week) to reduce the overall number of infusions, and increased volume at injection site(s) to reduce the number of injection sites. These modifications may reduce dosing commitments by shortening infusion times or increasing time intervals between infusions or decreasing injection sites, which may correlate to increased drug compliance.

Experience has shown that replacement therapy with immunoglobulins is lifesaving. If replacement is started early, and if appropriate amounts are given with sufficient frequency, the cycle of recurrent infections and progressive lung damage can be arrested. Near to normal serum IgG levels can be easily maintained.

Post-dose peak levels of SCIG are usually reached 3 to 6 days after infusion. It has been shown that after infusion, exogenous IgG is distributed relatively rapidly between plasma and extravascular fluid until approximately half is partitioned in the extravascular space. Therefore, a rapid initial drop in serum IgG is to be expected.

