After completing the Screening Period during which they will be assigned to 1 of the 3 study cohorts, patients will enter a 4-week Stabilization Period. During the Stabilization Period, patients will receive CUTAQUIG infusions at the same body-weight dependent dose and infusion rate as their previous SCIG product prior to entering the Treatment Period; however, this flow rate should not exceed maximum infusion rates listed in protocol (Section 5.5.3). Patients will receive 4 CUTAQUIG infusions during the Stabilization Period. Patients entering the study currently active and established on CUTAQUIG in Study SCGAM-03 will have already been stabilized on CUTAQUIG and will go directly into the Treatment Period following the Screening Visit. Patients that completed the SCGAM-03 study and went on a commercial SCIG product prior to entering SCGAM-06 are required to enter the Stabilization Period. During the Treatment Period, patients will receive CUTAQUIG infusions according to their assigned-cohort infusion parameters.

Throughout the study, the following interventions and procedures will be performed at predefined time points (Section 6.1.2 and the Flow Charts of Assessments Table 1 [Screening and Stabilization Periods], Table 2 [Cohort 1], and Table 3 [Cohort 2], Table 4 [Cohort 3]): blood draws for laboratory assessments, body weight measurement, patient diary review, physical examination including vital signs, local infusion-site reaction assessments, urine sampling, urine pregnancy tests, QoL assessments, and the Subject Questionnaire. AEs and any changes in concomitant medications will be recorded throughout the study period.

Patients who enter and participate in one cohort may not enter another cohort at a later time.

An Independent Data Monitoring Committee (IDMC) will periodically review relevant data throughout the study with emphasis on adverse events including serious adverse events and thromboembolic events.

The study will be conducted at study sites in the USA.

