6.1.5 Time Windows Used in this Study, including Tolerances

In this study, the following time windows and tolerances apply:

Table 7: Study Visit Times and Windows Used in this Study

Time point	Time stated	Tolerance
Stabilization Period Week 0: Cohort 1 and Cohort 2	1 week after Screening Visit	± 2 days
Stabilization Period Week 0: Cohort 3	2 weeks after Screening Visit	± 2 days
Treatment Period Baseline Visit	4 weeks after Stabilization Period Week 0	± 3 days
Treatment Period required on-site visits: Cohort 1 and Cohort 2	Weeks 4, 8, 12, and 24	± 1 week
Treatment Period required on-site visits: Cohort 3	Weeks 4, 12, and 24	± 1 week
Treatment Period optional on-site visits: all cohorts	Weeks 16, and 20	± 1 week
Interval between Last Treatment Visit and (Early) Termination Visit: Cohort 1 and Cohort 2	1 week	± 2 days (and prior to another IgG product)

Time point	Time stated	Tolerance
Interval between Last Treatment Visit and (Early) Termination Visit: Cohort 3	2 weeks	± 2 days (and prior to another IgG product)
Blood and urine sampling	Before IMP administrations conducted at the study site	none
CUTAQUIG infusions at patient's home	Every week (every 7 days), or Every other week (every 14 days) at double the weekly dose	±2 days ±2 days

Study visit days and windows/tolerances are not additive, but always refer back to the first visit time point for each study period.

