6.2 Duration of Study

6.2.1 Planned Duration for an Individual Patient

The duration for each patient in the study will be approximately 30 to 32 weeks: approximately 1 to 2 weeks in the Screening Period, 4 weeks in the Stabilization Period, 24 weeks in the Treatment Period, and 1 to 2 weeks to Termination Visit.

Patients entering the study established on weekly SCIG infusions will have a 1 week Screening Period. Patients entering the study established on every other week dosing will have a 2 week Screening Period.

Patients entering the study currently active and established on SCGAM-03 CUTIQUIG will skip the 4 week Stabilization Period.

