9.2 Statistical Analysis

All data collected will be listed and presented descriptively in full detail, by cohort as well as in total, to facilitate comparison between the different dosing regimens.

As detailed in Section 9.1, the change in total IgG trough levels when switching from weekly to bi-weekly infusions will be tested in Cohort 3 by means of a one-sided, paired t-test at the $\alpha=0.025$ level of significance.

Descriptive summaries will be presented for each of the primary and secondary variables according to their individual data types. The results of this study will be presented at the descriptive level only; any additional p-value or confidence interval presented is to be understood in the exploratory sense.

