3.2. Study Endpoints (Target Variables)

3.2.1. Primary Target Variables

The co-primary objectives are to compare total IgG trough levels from weekly infusions to every other week infusions and to assess safety and tolerability of increased infusion volumes and increased infusion rates at each infusion site and every other week dosing. These will be assessed using the following variables:

- Change in individual total IgG trough levels from weekly infusions to every other week infusions (Cohort 3)
- Occurrence of treatment-emergent AEs (TEAEs) throughout the entire Stabilization and Treatment Periods starting with the first infusion of IMP
- Occurrence of TEAEs temporally associated with CUTAQUIG delivered during the Treatment Period
- Occurrence of TEAEs temporally associated with CUTAQUIG delivered during the Stabilization Period
- TEAEs by speed of infusion
- Local infusion-site reactions
- Laboratory parameters (hematology, clinical chemistry, urinalysis)

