Cohort 2 (increased infusion rate - patients will receive CUTAQUIG weekly and increase infusion rates every 4 weeks): Patients will return to the clinic for the Treatment Period Baseline Visit, at which they will receive the same body-weight dependent (mg/kg) dose of CUTAQUIG but the infusion rate per site will be increased by up to 25 mL/hr/site for patients ≥ 40 kg or 10 mL/hr/site for patients < 40 kg. Patients will receive this new flow rate for 4 weekly infusions (Treatment Period Baseline and Weeks 1, 2, and 3), and return to the clinic at Week 4 for their next infusion at an increased infusion rate. This cycle will continue, with flow rates increased up to 25 mL/hr/site for patients ≥ 40 kg or 10 mL/hr/site for patients < 40 kg every 4th infusion until reaching either a maximum flow rate (100 mL/hr/site) or maximum tolerated flow rate (maximum flow rate based on Investigator's decision of patient's tolerance) is reached.

Cohort 3 (every other week dosing - patients will receive CUTAQUIG every other week at the equivalent of twice their weekly body-weight dependent [mg/kg] dose): Patients will return to the clinic for the Treatment Period Baseline visit to receive their first double mg/kg weekly dose and begin an every other week dosing schedule. Infusion volumes increases per site must not exceed 25 mL at the Treatment Period Baseline visit. If a patient's doubling of their weekly dose requires dosing with a volume of more than 25 mL per injection site, then they will be required to increase the number of infusion sites to remain below the maximum of 25 mL/site volume increase. If this occurs, after 2 infusions the patient may remove one of the newly introduced injection sites as long as the 25 mL/site increase limit is not exceeded.

Approximately 65 patients between the ages of ≥ 2 years and ≤ 75 years are planned for enrollment for the study into one of the following three cohorts:

- At least 15 patients in Cohort 1

- At least 15 patients in Cohort 2
- At least 35 patients in Cohort 3

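### Counts and patient incidence of temporally associated TEAEs are not comparable between weekly and every-other-week dosing, because the fixed 72-hour window covers about 43% of time on one regimen and 21% on the other

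*SAP*

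**What the plan says.** SAP 10.1 states that each "TEAE will be classified as temporally associated if the onset is during the infusion or within 72 hours after the end of the infusion". SAP 7.4 and Protocol 9.2.3.1 give the same window, and no section adjusts it for the dosing interval. The interval does differ: Protocol 6.1.5 (Table 7) gives home infusions as "Every week (every 7 days), or Every other week (every 14 days) at double the weekly dose", and in Cohort 3 "patients will receive CUTAQUIG every other week at the equivalent of twice their weekly body-weight dependent [mg/kg] dose" (SAP 3.3).

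The co-primary variables in SAP 3.2.1 include "Occurrence of TEAEs temporally associated with CUTAQUIG delivered during the Treatment Period" and a matching variable for the Stabilization Period. A further co-primary variable is all TEAEs over both periods, with no window. Protocol 9.2 has the data presented "by cohort as well as in total, to facilitate comparison between the different dosing regimens".

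Temporally associated TEAEs are summarised in three ways:
- as a number of events for each cohort (Protocol, Study Outline, Statistical Analysis Plan);
- as patients with any such event, and patient incidence by system organ class and preferred term, separately for Stabilization and Treatment (SAP 10.1);
- per infusion, as a percentage of infusions (SAP 10.1) and as each patient's ratio of affected to total infusions with a confidence limit (SAP 7.4 and 10.2).

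Infections have their own person-year rates, by period and without the window (SAP 9).

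**The concern.** Classification depends on onset time alone, and SAP 10.2 states that events judged unrelated are included. Background events therefore enter the variable in proportion to the time the window is open. That share halves when a Cohort 3 patient moves from weekly to every-other-week dosing, and it is half that of Cohorts 1 and 2 throughout treatment.

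Tolerability of every-other-week dosing is a co-primary objective, and the tables are meant to support comparison between regimens. A reader who sets the 72-hour counts or patient incidences side by side could credit every-other-week dosing with better tolerability that comes only from a shorter share of observed time. The window also leaves 11 of every 14 days after a doubled dose outside these tables, against 4 of every 7 days on weekly dosing.

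**Working it through.** The documents state no coverage figure, so there is none to reproduce. The inputs are:
- **Window:** 72 hours after the end of infusion (SAP 10.1).
- **Intervals:** 7 and 14 days (Protocol Table 7).
- **Duration:** "24 weeks in the Treatment Period" (Protocol 6.2.1). With infusions from Baseline to Week 24, this gives 25 weekly or 13 every-other-week infusions. The Termination Visit is 1 or 2 weeks after the last infusion, so the spans are 175 and 182 days.
- **Stabilization:** "Patients will receive 4 CUTAQUIG infusions during the Stabilization Period" (Protocol 3.2), over 28 days.
- **Background rate:** an assumption. Protocol 1.1 gives 3.43 infections per person-year in an earlier study of the product and 2 to 5.18 across SCIG studies. These stand in for events unrelated to infusion; 1, 12 and 24 are added to widen the range.

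**Step 1, coverage.** Window hours / interval hours: 72/168 = 42.9% weekly; 72/336 = 21.4% every other week; ratio 0.50. Adding assumed infusion times (1 to 4 hours weekly, 1 to 8 hours every other week) gives 43.5–45.2% and 21.7–23.8%, ratio 0.50–0.53.

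**Step 2, window-days.** Infusions × 3 days:
- Weekly treatment: 25 × 3 = 75 of 175 days (43%).
- Every-other-week treatment: 13 × 3 = 39 of 182 days (21%).
- Stabilization: 4 × 3 = 12 of 28 days (43%).

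**Step 3, background events only, no true difference.** Expected count = rate × window-days / 365.25. Patient incidence = 1 − exp(−expected count). The count ratio is 39/75 = 0.52 at any rate.

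| Rate per person-year (assumed) | Weekly incidence | Every-other-week incidence | Incidence ratio |
|---|---|---|---|
| 1 | 18.6% | 10.1% | 0.55 |
| 2 | 33.7% | 19.2% | 0.57 |
| 3.43 | 50.6% | 30.7% | 0.61 |
| 5.18 | 65.5% | 42.5% | 0.65 |
| 12 | 91.5% | 72.2% | 0.79 |
| 24 | 99.3% | 92.3% | 0.93 |

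Without the window, at 3.43 per person-year, incidence over 175 and 182 days is 81% and 82%.

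**Step 4, infusion-triggered events.** Count ratio = (13/25) × k, where k is the risk per infusion at the doubled dose relative to the weekly dose: 0.52 for k = 1, 0.78 for k = 1.5, 1.04 for k = 2. If half of the weekly events are infusion-triggered and k = 2, the overall ratio is 0.5 × 0.52 + 0.5 × 1.04 = 0.78.

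**Step 5, per infusion.** The window is 72 hours under both regimens. The background probability per infusion is 1 − exp(−3.43 × 3/365.25) = 2.8% in each, so the per-infusion rates show no artificial difference.

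**The case against.** The strongest reply is that the SAP already holds the remedy. Its per-infusion rates put the window on an equal footing, and the all-TEAE co-primary variable, summarised by cohort, has no window. That is correct, and it limits the point to the count and incidence tables. It does not close the gap. The per-infusion rates still leave out onset after 72 hours, and SAP 10.2 states no split by period, so as written Cohort 3's ratio can pool 4 weekly with 13 every-other-week infusions. The all-TEAE variable runs over both periods together, so it cannot isolate the switch from weekly dosing.

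A reader might infer more than the documents support:
- **That Cohort 3's TEAE count halves by construction.** Only the temporally associated variables are affected, and only for events unrelated to infusion timing. Fewer infusion-triggered events because there are fewer infusions is a real effect of the regimen; reducing the number of infusions is one of its stated aims (Protocol 1.2).
- **That Cohort 3 would look twice as well tolerated.** Patient incidence falls by less than half at every rate tried.
- **That a falling weekly rate would be displayed at the switch.** No such rate is planned. Patient incidence by period would rise in Cohort 3, from about 11% (12 window-days) to 31% (39 window-days) at 3.43 per person-year, because treatment is longer.
- **That late events reach no period-specific table.** Infections do, through SAP 9.
- **That the window misses the IgG peak.** Protocol 1.2 says "Post-dose peak levels of SCIG are usually reached 3 to 6 days after infusion", but Protocol 1.1 puts the peak at 48 to 72 hours, inside the window. The two sections disagree, so the argument carries no weight.

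Two further replies stand. The detailed table list is a separate document (SAP 2 and 13), so the gap is in what SAP 10.1 names and may not be in what is finally produced. The analysis is also descriptive, with cohorts chosen by preference; only the Cohort 3 trough change is tested.

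**Conclusion.** The point holds for counts and patient incidence of temporally associated TEAEs. With coverage of 43% against 21% of time, these are not comparable between weekly and every-other-week dosing. The coverage figures follow from the documents at nominal intervals, ignoring infusion duration. The background count ratio of 0.52 assumes a constant event rate unrelated to infusion and full follow-up. The incidence ratios of 0.55 to 0.93 also depend on the assumed rates of 1 to 24 per person-year. For infusion-triggered events the documents give no risk per infusion at the doubled dose, so 0.52 to 1.04 is a range for k from 1 to 2 and not an estimate.

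What is missing is narrow. SAP 10.1 lists no all-TEAE safety table split by period or expressed per person-time. TEAEs with onset after 72 hours on the every-other-week regimen therefore cannot be compared with Cohort 3's own weekly Stabilization Period, infections excepted. No hypothesis test is affected, and this ranks as an inexpensive improvement.

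**What to change.** Keep the 72-hour and per-infusion tables. In SAP 10.1:
- add a table of all TEAEs, without the window, as events per patient-week, by cohort and by Stabilization and Treatment Period;
- footnote the 72-hour count and incidence tables with the share of time covered (about 43% weekly, 21% every other week);
- state that regimen comparisons rest on the all-TEAE person-time rates, read with the per-infusion rates.

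Optional: a tabulation by days since last infusion (0–3, 4–7, 8–14), and the per-infusion rate split by period for Cohort 3.

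The cost is SAP wording and one added descriptive table, with a second if the optional tabulation is included. Infusion dates and event onset relative to infusion are already planned for capture or derivation. The downsides are modest. All-TEAE rates carry more background events. Patients entering directly from SCGAM-03 skip Stabilization and contribute no weekly reference period. The comparison between cohorts remains descriptive and non-randomised.

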
Test Product, Dose, and Mode of Administration:
 
CUTAQUIG, human normal immunoglobulin for subcutaneous (SC) administration.
 
CUTAQUIG will be administered by SC infusion every week (± 2 days, Cohort 1 and Cohort 2), every other week (± 2 days, Cohort 3) at the doubled weekly dose. The dosing frequency will be determined by cohort assignment.
 
Patients will receive the same mg/kg body weight dose as their previous SCIG product prior to study entry.
 
If, during the study, a patient's body weight changes by $>5\%$ from the first infusion of IMP, the dose will be adjusted to keep a constant mg/kg body weight basis. Additional adjustments will be made by the Investigator at study visits if the patient's body weight changes $>5\%$ from the previous adjusted weight.
 
Each patient's CUTAQUIG dose may be individualized, if considered necessary by the Investigator, by titrating upward or downward.
 
Batch (lot) numbers will be reported in the final report of the study.

Duration of Treatment:
 
Individual patient participation will be approximately 30 to 32 weeks:
 
• Screening Period: 1 to 2 weeks*• Stabilization Period: 4 weeks**• CUTAQUIG Treatment Period: 24 weeks (6 months)• Termination Visit: 1 week after last CUTAQUIG infusion for Cohort 1 and Cohort 2; 2-weeks after last CUTAQUIG infusion for Cohort 3

Name of Sponsor/Company: Octapharma USA, [name]	
Name of Investigational Product: CUTAQUIG	Protocol Identification Code: SCGAM-06
Name of Active Ingredient: Human Normal Immunoglobulin	Date of Final Protocol: 28-Aug-2019

* Patients entering the study established on weekly SCIG infusions will have a 1-week (± 2 days) Screening Period. Patients entering the study established on every other week dosing will have a 2-week (± 2 days) Screening Period.

** Patients entering the study currently active and established on CUTAQUIG in Study SCGAM-03 will skip Stabilization Period.

Reference Therapy, Dose, Mode of Administration:

Not applicable.

Study Outcome Parameters (Primary and Secondary Endpoints):**Primary Endpoint Parameters:**

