3.3.2 Dosing

Stabilization Period: CUTAQUIG will be administered subcutaneously every week (± 2 days).

Treatment Period: CUTAQUIG will be administered subcutaneously every week (± 2 days) (or every other week [± 2 days], if applicable) for Cohort 1 (increased infusion volume) and Cohort 2 (increased infusion rate). For Cohort 3, CUTAQUIG will be administered every other week (± 2 days) at double the weekly dose.

Cohort 1 (increased volume at each infusion site – patients will receive CUTAQUIG weekly and increase infusion volumes every 4 weeks): Patients will return to the clinic for the Treatment Period Baseline Visit, at which they will receive the same body-weight dependent (mg/kg) dose but the volume will be increased by up to the maximum allowed volume increase per infusion site of 25 mL/site for patients ≥ 40 kg or 10 mL/site for patients < 40 kg. This volume increase per infusion site can be achieved by reducing the total number of injection sites while keeping the same or lower flow rates as received with their prior treatment. When introducing increased volumes to an infusion site, Investigators must attempt to maintain flow rates similar to or lower than prior infusions. This may require adjusting pump rate, tubing size, needle gauge, etc. Patients will receive this new volume per site for 4 weekly infusions (Treatment Period Baseline and Weeks 1, 2, and 3), and return to the clinic at Week 4 for their next infusion at an increased volume at each infusion site. This cycle will continue, with infusion volumes increasing by up to a maximum allowed volume increase per infusion site of 25 mL/site for patients ≥ 40 kg or 10 mL/site for patients < 40 kg every 4th infusion until reaching a patient's maximum dose (in mL), maximum tolerated volume (maximum volume based on Investigator's decision of patient's tolerance), or 100 mL.

at 1 injection site – whichever is reached first. For patients with maximum volume that exceeds 100 mL at 1 injection site, 2 injection sites should be used.

The following change in volume increments should be followed:

- Baseline: Reduce the number of injection sites by 1 (eg, patients using a 4 needle set will reduce to a 3 needle set). Tubing set, needle gauge, and pump rates (if applicable) may be adjusted to minimize flow rate variations. Investigators must ensure minimal flow rate changes at each injection site when increasing volume. Continue with the same infusion parameters at Weeks 1, 2, and 3.

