where T_{eow} is the mean total IgG trough on steady-state dosing every other week, T_w is the same for weekly dosing, and a maximum decrease of 1 g/L for the mean total IgG trough level is considered acceptable.

T_w will be determined after completion of the Stabilization Period, T_{eow} at a given subject's final study visit where a valid IgG trough level is collected and reported within a suitable visit window. If a subject terminates from the study prior to the end of study visit (2 weeks following Week 24 infusion), or if a completed subject's end of study IgG trough is not valid or not collected, then the last study visit where a valid IgG trough level was collected will be considered T_{eow} .

This one-sided hypothesis will be tested by a paired t-test at the alpha=2.5% level of significance. Assuming 3.0 for the standard deviation common to both members of a pair, and 0.8 as the correlation between members of a pair, this results in a required minimum of 31 evaluable patients to achieve a power of 80%.

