10.2. Infusions with One or More Temporally Associated AEs

The number of infusions with at least one temporally associated adverse event (including AEs judged not to be related to *CUTAQUIG* by the investigator) over the total number of infusions will be calculated for each patient, and the ratio will be presented, including the associated upper one-sided 95% confidence limit. The calculation of this confidence interval will take into account the observed intra-patient correlation - this is necessary because each patient may experience more than one infusion with an associated AE; it can therefore not be assumed that the observed events are statistically independent.

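### Temporally associated TEAEs are split by period only as patient incidence or raw counts, over 4 versus 13 or 25 infusions; the planned per-infusion ratio is not split by period

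*SAP*

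**What the plan says.** SAP 3.2.1 lists temporally associated TEAEs among the primary target variables once for each period; the stabilization entry reads "Occurrence of TEAEs temporally associated with CUTAQUIG delivered during the Stabilization Period".

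In SAP 10.1 these become two rows in a list of patient counts, "Any Temporally Associated TEAE during Stabilization Period" and "Any Temporally Associated TEAE during Treatment Period". They also become two patient-incidence tables by system organ class and preferred term, one for each period. The statistical part of the protocol synopsis adds the number of such events in each period, by cohort and overall, with no exposure denominator.

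A per-infusion measure is also planned. SAP 7.4 defines it for each patient as infusions with at least one temporally associated AE divided by infusions started. SAP 10.1 lists a corresponding percentage table. SAP 10.2 takes affected infusions "over the total number of infusions will be calculated for each patient" and adds an upper one-sided 95% limit that allows for intra-patient correlation. None of the three names a period. SAP 7 sets the general breakdown as overall and by cohort, and the default percentage denominator as everyone in the analysis population.

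**The concern.** The trial has no control group and no randomization. The Stabilization Period, on the patient's previous dose and flow rate, is the only reference on the study product within the same patients. With a stabilization row and a treatment row in one summary table, a reader will compare them.

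The chance that a patient has at least one event grows with the number of infusions, and the two periods differ several-fold in that number. Tolerability could be unchanged after the switch and the treatment row would still be higher. A real improvement could be hidden for the same reason. These are co-primary tolerability variables, so the display should be able to tell a change in risk from a change in exposure.

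**Working it through.** **The plan's own figures.** The documents give no AE incidence or AE precision figure to reproduce. Their one calculated design figure, 31 evaluable Cohort 3 patients for the IgG test, does reproduce: the SD of the difference is 3.0 × √(2 × (1 − 0.8)) = 1.897, and power for a 1 g/L shift is 0.797 at n = 30 and 0.810 at n = 31. It has no bearing on this point.

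**Infusions per patient, full schedule.**
- Stabilization: protocol 3.2 says "Patients will receive 4 CUTAQUIG infusions during the Stabilization Period", so k = 4.
- Treatment, Cohorts 1 and 2: weekly from Baseline (Week 0) through Week 24. An infusion is given at Week 24: the protocol flow charts schedule one, and SAP section 5 places the Cohort 3 end-of-study visit "2 weeks following Week 24 infusion". So k = 25.
- Treatment, Cohort 3: protocol 3.3.2 says "For Cohort 3, CUTAQUIG will be administered every other week (± 2 days) at double the weekly dose". Weeks 0, 2, …, 24 give k = 13.
- Exposure ratio to stabilization: 13/4 = 3.25 and 25/4 = 6.25.

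**Patient incidence at the same per-infusion risk p in both periods.**
- Independent infusions: 1 − (1 − p)^k. For p = 0.10 and k = 4, 1 − 0.9^4 = 34.4%.
- Correlated infusions (beta-binomial, intra-patient correlation ρ): with a = p(1/ρ − 1) and b = (1 − p)(1/ρ − 1), incidence is 1 − ∏(b + j)/(a + b + j) over j = 0, …, k − 1. For p = 0.10 and ρ = 0.3, a = 0.233 and b = 2.1. For k = 4 the product is 0.900 × 0.930 × 0.946 × 0.956 = 0.757, giving 24.3%.

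The values of p and ρ are assumptions. The one range in the documents is for local reactions, 0.028 to 0.697 per infusion (protocol 1.1), and its two ends are included.

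| p | ρ | Stabilization (4) | Cohort 3 treatment (13) | Cohorts 1 and 2 treatment (25) |
|---|---|---|---|---|
| 0.028 | 0 | 10.7% | 30.9% | 50.8% |
| 0.05 | 0 | 18.5% | 48.7% | 72.3% |
| 0.10 | 0 | 34.4% | 74.6% | 92.8% |
| 0.697 | 0 | 99.2% | 100% | 100% |
| 0.028 | 0.3 | 7.3% | 12.8% | 16.1% |
| 0.10 | 0.1 | 30.4% | 57.9% | 71.9% |
| 0.10 | 0.3 | 24.3% | 39.3% | 47.1% |
| 0.10 | 0.5 | 19.4% | 27.8% | 32.3% |
| 0.697 | 0.3 | 93.3% | 98.7% | 99.5% |

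**Raw event counts behave in the same way.** At p = 0.10 and one event per affected infusion, the expected counts per patient are 0.4, 1.3 and 2.5.

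**What the unsplit ratio can show.** Treatment supplies 13/17 = 76% of a Cohort 3 patient's infusions and 25/29 = 86% of those of a patient in Cohort 1 or 2. Suppose risk doubled from 5% to 10% at the switch. The pooled ratio would be (4 × 0.05 + 13 × 0.10)/17 = 8.8% or (4 × 0.05 + 25 × 0.10)/29 = 9.3%. One figure of this kind cannot show that anything changed. Split by period, the ratio would be 5% and 10%; with unchanged risk it would be p in both periods.

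**Denominator.** Patients rolling over directly from SCGAM-03 skip stabilization. Their number is not given. If they were 20% of the set and stayed in the denominator, 34.4% would fall to 0.8 × 34.4 = 27.5%.

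**The case against.** Four objections deserve weight.

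- **No comparison between periods is prespecified.** A reader might infer that the plan formally compares stabilization with treatment. It does not. Apart from the Cohort 3 IgG test, the analysis is descriptive. This stands: the point is about how adjacent rows will be read, and no test or sample size depends on it.
- **Exposure-adjusted output is already planned.** A reader might infer that nothing in the plan is like for like, or that Cohort 3 will look better merely because it has about half the infusions. The documents do not support that. The per-infusion percentage falls under the by-cohort rule of SAP 7 and largely answers the comparison between cohorts. SAP 10.1 also plans tables by total flow rate, and by flow rate and number of lines. Their counting unit is not stated, and they are organised by rate, not by period. SAP 8.4 summarises infusions administered, again with no period named.
- **A period split is not excluded.** The table list is deferred to a separate document, which could add one. That is true, but the SAP text does not commit to it.
- **Independence exaggerates the effect.** SAP 10.2 itself says events within a patient cannot be taken as independent. This also stands. At p = 0.10, moving from ρ = 0 to ρ = 0.3 cuts the gap from stabilization from 40 to 15 percentage points in Cohort 3, and from 58 to 23 in Cohorts 1 and 2. The distortion shrinks but remains.

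**Conclusion.** The point holds for the comparison between periods only. Patient incidence and raw counts by period mix risk with an exposure ratio of 3.25 or 6.25, and the one measure that separates them is not split by period.

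The size depends on assumptions the documents do not settle. At a constant 10% per-infusion risk and full schedules, stabilization, Cohort 3 and Cohorts 1 and 2 would show 34%, 75% and 93% under independence, or about 24%, 39% and 47% at a correlation of 0.3. A reader might infer that treatment must always look much worse. That does not follow: near the top of the protocol's quoted range all periods are close to 100%, and the measure then stops discriminating. Nor does a higher treatment figure arise from exposure alone unless per-infusion risk is in fact unchanged.

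The SAP already shows infection rates per person-year separately for stabilization and treatment (SAP 9), so the same approach here would be consistent with its own practice. This is an inexpensive reporting improvement.

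**What to change.** In SAP 10.1 and 10.2, present the per-infusion ratio separately for the Stabilization and Treatment Periods within each cohort. Attach the correlation-adjusted upper limit already planned, and place the result beside the patient-incidence tables, which can stay.

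State that stabilization denominators include only patients infused in that period; direct SCGAM-03 roll-overs have no such infusions.

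If a within-patient difference is added, make it supportive and limit it to patients with both periods. Label it with two caveats: most entrants change product at the start of stabilization, and the order of the periods is fixed. Both are confounded with the change of regimen. In Cohorts 1 and 2 a single treatment figure also averages over successive escalation steps.

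The cost is a few more tables. No new data and no design change are needed.
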